3.0 OBJECTIVES

PRIMARY

The primary objective of this study is:

- To compare the clinical outcomes of Knee Replacement surgery using the Oxford Knee Score (OKS) at 24 months, in patients receiving Bicompartamental Knee Replacement using Restoris MCK Multicompartmental Knee System with Stryker's robotic-arm assisted surgery system Mako, to Total Knee Replacement using the Triathlon Total Knee System performed with Stryker's robotic-arm assisted surgery system Mako.

SECONDARY

The secondary objectives of this study are:

- To determine functional and clinical outcomes of Bicompartamental Knee Replacement (BKR) and Total Knee Replacement (TKR) (including pain, function and health-related quality of life) with Restoris MCK Multicompartmental Knee System and Triathlon Primary Total Knee System at 24 months via:
 - EQ-5D: The EQ-5D is a standardised instrument for use as a measure of health outcome.
 - VAS Pain: A graphical Visual Analog Scale that patients use to indicate their level of pain.
 - New Knee Society Score 2011 (KSS): A validated score assessing surgeon generated objective measures based on technical outcomes, and subjective measures based on patient satisfaction, patient expectations and functional activity of the knee (Noble et al. 2012) (Scuderi et al. 2012).
 - Forgotten Joint Score (FJS): The Forgotten Joint Score is a newly-developed twelve-item, self-reported assessment of how aware recipients

of hip and knee joint replacement are of their joint in everyday life (Behrend et al, 2011).

- To compare incidence of loosening, reoperation and revision in patients receiving Restoris MCK Multicompartmental Knee System, compared to Triathlon Total Knee System.
- To determine length of hospital stay in patients receiving Restoris MCK Multicompartmental Knee System, compared to Triathlon Total Knee System.

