11.0 EVALUATIONS

All data will be recorded on Case Report Forms or via Electronic Data Capture (EDC). The surgeon or study coordinator will complete and sign forms at the time of each protocol required visit.

The following data will be collected for all patients:

- **Patient Demographics:** A record of the patient's date of birth, gender, height, and weight will be obtained pre-operatively.
- **Medical History:** Relevant medical history will be recorded pre-operatively.
- **Surgical Details:** A summary of the surgical procedure will be collected during the operation. This will include details of the prosthetic components implanted, operating time and comments.
- **Patient outcome measurements:** Surgeon assessment of patient clinical outcomes will be recorded at various study visits. The following outcome scores will be recorded at time points as set out in the patient evaluation schedule. These include pre-operative, 6 week, 3 month, 12 month and 24 month follow-up visits (see Appendix 3):
 - **Oxford Knee Score (OKS):** A 12 item questionnaire was developed to measure outcomes of patients undergoing total knee replacement (Dawson et al. 1998). The score is a self-completed questionnaire that asks patients to answer questions on their pain levels and function (Whitehouse et al. 2005).
 - **EQ-5D Euro-Qol (EQ-5D-5L):** The EQ-5D-5L is a standardised patient-completed instrument for use as a measure of health outcome (Fransen and Edmonds, 1999). It consists of 5 dimensions: mobility, self care, usual activities, pain/discomfort, and anxiety/depression. There are 5 levels of severity to select from within each dimension.

- **VAS Pain:** A graphic Visual Analogue Scale (VAS) used as measurement instrument for patients to indicate their level of pain. The amount of pain that a patient feels is believed to range across a continuum from none to an extreme amount of pain i.e. from the patient's perspective this spectrum appears continuous - their pain does not take discrete jumps, as a categorization of none, mild, moderate and severe (Wewers et al. 1990).

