12.4 Statistical Analysis

For each treatment group the demographic data will be summarised as number of observations, mean, standard deviation, minimum, median, maximum for continuous variables such as age, and as frequency and percentage for categorical variables such as gender.

For the test of the treatment effect the null hypothesis is no difference between the means of the 2 treatment groups, and will be tested against the alternative hypothesis that there is a difference between the means of the treatment groups.

The primary and continuous secondary efficacy variables will be analysed with a mixed model for repeated measurements (MMRM). The model will include factors for treatment group, time, and the interaction between treatment group, and time. For each variable the baseline values will be included in the model as covariate. The treatment effect will be tested against between patient variance. The time effect, and the interaction between treatment group and time will be tested against within patient variance. The results will be summarised as mean, and 95% CI by treatment group, and time. The least squares means will be reported for the treatment difference at each time, and overall with 95% CI. The results will be presented in tabular format, and graphically by treatment group, and time. The continuous variables of change from baseline, and percentage change from baseline will be reported as mean, and 95% CI for each treatment group.

Adverse events will be tabulated separately and reviewed for any commonalities.

The data will be summarised and comparisons presented according to:

<http://sspnet/sites/raqa/qms/documents/FM-CRD-029.docx>

MAKORCT-15 Final version 5.0 22 February 2018

- Treatment group : Restoris® MCK Multicompartmental Knee System or Triathlon Primary Total Knee System
- Adverse events: General complications, local complications, device-related complications, revisions/removals, loosening and pain.

In the event of errors in randomisation, the patient will be classified according to the treatment received. All randomisation inconsistencies will be listed.

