12.5 Analysis Populations

Intent to Treat Populations

An intent-to-treat analysis will be performed using all patients who were randomised and received a study device. Patients missing the measure of the primary end point (i.e. completed surgery and did not attend the 24 month visit) will be considered missing in the intent to treat analysis; no imputation of missing data will be conducted for any variables.

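### Section 12.4 tests a treatment effect with no visit attached, in effect an average over follow-up, while the primary objective is the Oxford Knee Score at 24 months

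*Combined protocol and SAP*

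**What the plan says.** Section 3.0 sets the primary objective: "To compare the clinical outcomes of Knee Replacement surgery using the Oxford Knee Score (OKS) at 24 months". The functional and clinical secondary scores are tied to the same visit ("Restoris MCK Multicompartmental Knee System and Triathlon Primary Total Knee System at 24 months via"). Section 12.5 also identifies the primary end point with the 24-month visit, in its rule on missing data: "Patients missing the measure of the primary end point (i.e. completed surgery and did not attend the 24 month visit".

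Section 12.4 names no visit for the hypothesis: "For the test of the treatment effect the null hypothesis is no difference between the means of the 2 treatment groups". It specifies a mixed model for repeated measurements (MMRM) with treatment, time, their interaction and the baseline value. It then assigns error terms: "The treatment effect will be tested against between patient variance", and "The time effect, and the interaction between treatment group and time will be tested against within patient variance". On output it says: "The least squares means will be reported for the treatment difference at each time, and overall with 95% CI".

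For the outcome scores as a group, section 11.0 gives the assessment times: "These include pre-operative, 6 week, 3 month, 12 month and 24 month follow-up visits". By the evaluation schedule in section 1.0, OKS is collected at all four of the post-operative times.

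**The concern.** Treatment, time and treatment-by-time are separate terms in the model. The treatment effect tested against between-patient variance is therefore most naturally the main effect, which is the group difference averaged over the post-operative visits. It is the only test of a between-group mean difference that 12.4 describes. The interaction test asks a different question: whether the difference changes over time.

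For OKS the plan yields five treatment differences (four visits and overall) and ranks none of them. If the two implants differ mainly in early recovery, the averaged test can be significant with no difference at 24 months. If they differ mainly late, it can miss a real 24-month difference. In either case the p-value from 12.4 and the 24-month confidence interval can point in opposite directions. The plan does not say which one answers the primary objective, nor what follows if the interaction is significant. The choice could then be made after the results are seen.

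**Working it through.** **Inputs from the documents.** Section 12.2: difference 6.0, SD 8.0, two-sided 0.05, 29 per arm for 80% power, raised by 20% to 35 per arm. Sections 1.0 and 11.0: four post-operative OKS visits.

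**Assumptions not in the documents.** SD 8 at every visit; equal correlation ρ between visits, 0.5 with range 0.4 to 0.7; equal visit weights (the usual least-squares-means definition); complete data on 29 per arm; no gain from baseline adjustment; the visit profiles below.

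**Step 1: the plan's own figure.** For a two-sample t-test at one time point, the noncentrality is 6 / (8 × √(2/29)) = 6 / 2.101 = 2.86 on 56 degrees of freedom. Power is 80.1%, and the exact requirement is 28.9, so 29 per arm. Then 29 × 1.2 = 34.8, so 35. The stated sample size reproduces, and it is that of a single two-group comparison.

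**Step 2: SD of the four-visit average.** SD = 8 × √((1 + 3ρ)/4), which is 5.93, 6.32, 6.69 and 7.04 for ρ = 0.4, 0.5, 0.6 and 0.7.

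**Step 3: power of each test.** At ρ = 0.5 the standard error of the averaged difference is 6.32 × √(2/29) = 1.661.

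| Difference at 6 weeks, 3, 12, 24 months | Average | Noncentrality, averaged test | Averaged test significant (ρ 0.4 to 0.7) | 24-month test significant |
|---|---|---|---|---|
| (a) 0, 2, 4, 6 | 3.0 | 1.81 | 43% (47% to 36%) | 80% |
| (b) 6, 4, 1, 0 | 2.75 | 1.66 | 37% (41% to 31%) | 5% |
| (c) 6, 6, 6, 6 | 6.0 | 3.61 | 94% (97% to 89%) | 80% |

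**Step 4: how often the verdicts differ.** In 40,000 simulated trials at ρ = 0.5, one test was significant and the other not in 39% of trials under (a) and 37% under (b). Under (c) the figure was 16%, nearly all of it the averaged test succeeding where the 24-month test missed.

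**Step 5: would the interaction test give warning?** Its noncentrality is (29/2) × Σ(d − mean d)² / (64 × (1 − ρ)), on 3 and 168 degrees of freedom. The sums of squares are 20 for (a) and 22.75 for (b). At ρ = 0.5:
- (a) 14.5 × 20 / 32 = 9.06, power 70% (62% to 91% over ρ 0.4 to 0.7)
- (b) 14.5 × 22.75 / 32 = 10.31, power 76% (68% to 95%)

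It would often flag the problem, but 12.4 attaches no consequence to it.

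**Step 6: sensitivity.** If baseline adjustment cut the SD to 7 (ρ = 0.5), the figures become 53% against 89% for (a) and 46% against 5% for (b). The pattern is unchanged.

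**The case against.** The strongest reply is that the documents already fix the target. The objective names 24 months. Section 12.5 treats a patient without the 24-month visit as missing, which fits a 24-month analysis better than an averaged one, since under an averaged test that patient's earlier visits would still count. Section 23.0 places the final analysis after all 24-month visits. Section 12.4 plans a 95% interval for the difference at each visit, and at 24 months that interval amounts to a two-sided 5% test. On this view only a label is missing. The sentence on variances may also be a generic description of the model's error terms, because 12.4 gives no visit weights or type of test.

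Much of this is fair. The right estimate is already planned, and the averaged reading is an inference, though the likely one. But the intent in 3.0 and 12.5 is exactly what 12.4 fails to carry through: its hypothesis and its treatment test name no visit, and no other section says that the 24-month contrast decides. A statistician following 12.4 literally would report the main-effect p-value. Visit weights other than equal would still not turn that average into the 24-month difference.

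Two further points stand. Profiles (a) and (b) were chosen to separate the two tests, so the percentages illustrate and do not predict. Scenario (c) favours the averaged test, and its 16% is not evidence of harm.

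**Conclusion.** The concern holds, and 12.4 is wrong as written: the one test of a between-group mean difference it describes addresses a different quantity from the stated primary objective. That conclusion rests on the text and on the usual reading of a main effect in a model that also contains time and treatment-by-time. The size of the consequence depends on an unknown visit profile. With the assumed late-emerging difference, power is 43% instead of 80%. With the assumed early-only difference, the averaged test is significant in 37% of trials instead of 5%. With a constant difference the averaged test has more power and the mismatch does little damage. This should be fixed before the analysis; it does not undermine the design or the sample size.

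**What to change.** Add to 12.4: the primary analysis is the bicompartmental minus total knee replacement least-squares-mean difference in OKS at 24 months from the MMRM, tested at two-sided 0.05; the overall difference, the earlier-visit differences and the treatment-by-time interaction are secondary and do not alter the primary test.

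Two changes follow from it:
- Use the 24-month contrast for the continuous secondary scores as well, since their objective is also at 24 months. With equal visit weights, an averaged effect would give that visit 1/4 of the weight for OKS, 1/3 for EQ-5D, VAS pain and the Forgotten Joint Score, and 1/2 for the Knee Society Score.
- Name the 24-month visit in 12.2, which now refers only to post-operative assessments in general.

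Optionally, state the covariance structure and degrees-of-freedom method, which 12.4 leaves open (for example, unstructured with Kenward-Roger).

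The cost is wording only, and N stays at 70. If the true difference is constant over time, the 24-month contrast gives up power relative to the average (80% against 94% at ρ = 0.5), but 80% is the power that 12.2 planned for.

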7.0 STUDY DESIGN

This is a prospective, randomised, study with patients treated at multiple hospitals.

Prior to each surgeon enrolling their first study patient, they must be accredited to perform Stryker's Robotic-arm Assisted Surgery. Accreditation includes attending a Surgical Skills training course provided by Stryker and led by a surgeon experienced with using Mako, review of the planning and surgical technique guides, surgical observation and consultation with current Mako users.

All potential study patients will be assigned a MAKORCT-15 study ID.

If a patient has previously had a MAKO CT Arthrogram and wishes to participate in the study, the patient is required to sign the study approved consent form and the previous MAKO CT Arthrogram will be used for study purposes.

If the patient has previously had a MRI or MRI/CT Arthrogram (within 6 months of planned study surgery date), the patient is required to sign the study approved consent form and the previous MRI or MRI/CT Arthrogram will be used for study purposes. Once the study consent form is signed, the patient will be referred for a MAKO CT for surgical planning purposes.

If a patient has not had a MAKO CT Arthrogram, MRI or MRI/CT Arthrogram and wishes to participate in the study, the patient is required to sign the study approved consent form, and once signed the patient will be referred for a MAKO CT Arthrogram.

<http://ssp.intranet/sites/raqa/qms/documents/FM-CRD-029.docx>

MAKORCT-15 Final version 5.0 22 February 2018

If the patient meets the Inclusion and Exclusion criteria and has signed the study consent form, the patient will be enrolled onto the study. If the patient does not meet the Inclusion and Exclusion criteria and has signed the study consent form, the patient will be terminated from the study as a Screen Failure.

Enrolled patients will be randomised to one of two equally sized groups either; the Restoris® MCK Multicompartmental Knee System group or the Triathlon Primary Total Knee System group. Randomisation will take place via the Investigator or designee using the central randomisation system within Inform for allocation to either group. Block randomisation will be performed by a statistician using specialised randomisation software with a block size of 4.

Any deviation from the assigned treatment will be reported as a deviation from Protocol.

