12.2 Sample Size Justification

The change in the Oxford Knee Score (OKS) from pre-op to post-op assessments has a standard deviation of approximately 8.0 (Scott et al, SD=9.8; Walker et al, Table 2, SD=6 for UKR, and SD=8 for TKR). The parameters of the sample size calculation were set as follows: level of significance 0.05, 2-sided test, and postulated difference and standard deviation of 6.0 and 8.0 respectively. For these settings a sample of 29 patients in each arm is required to achieve a power of 80%. The sample size was increased by 20% to 35 in each arm, so 70 in total, in order to allow for withdrawals.

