13.0 SELECTION CRITERIA FOR INVESTIGATORS AND CLINICAL MONITORS

- The Investigator/s selected to participate in this study is/are qualified Orthopaedic surgeon/s.
- Research assistants and study staff will be representatives of the Institute under the direction of the Principal Investigator.
- Any conflicts of interest (including financial assistance from other parties) will be declared by Investigators and research personnel before the commencement of the trial.
- Investigators must maintain a list of any delegated duties with respect to the trial, and the persons and qualifications of those persons to whom the duties are assigned.
- Sites must be able to demonstrate that adequate subject recruitment is likely to be possible, with necessary time available to conduct the study to GCP requirements, and with adequate facilities and trial staff.

- Investigators must provide medical care to a trial participant that is necessary as a result of any adverse event experienced during or following the trial that is deemed related to the trial.
- Investigators must possess, prior to trial commencement, a favorable Ethics Committee endorsement of trial protocol, Patient Information and Consent forms and any other information given to subjects.
- All trial related documents are subject to Ethics Committee review. A regular trial report is also mandatory for provision to the Ethics Committee (in accordance with local requirements).
- The Investigator/Institution shall permit trial related monitoring, audits, Ethics review and regulatory inspections, by providing direct access to source data/documents and any other trial related documentation.
- The trial **MUST** be conducted according to the approved protocol.
- Any deviation from the protocol must be documented for later review.
- No deviation from protocol may occur without Ethics Committee endorsement, unless it is required to prevent imminent harm to participants
- Investigators must ensure subjects have given informed, written consent, with all trial procedures and risks adequately explained.

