17.2 Withdrawal from Study

Participants will be advised that they may voluntarily withdraw from the study at anytime, for any reason and they are not obligated to reveal the reason to the Investigator and it will not affect their medical care. However, in such cases, appropriate effort will be made to determine the reason for withdrawal from the study. The Investigator may request a letter from the patient noting his or her desire to withdraw from the study. All attempts to locate participants lost to follow up will also be documented.

Participants will be informed that should they withdraw from the study they should remain under the care of an appropriately experienced physician until the physician deems further follow-up unnecessary.

The following are circumstances for which a patient would be identified as not continuing their participation in the study:

- Study Completed / Terminated
- Screen Failure
- Death
- Unable to Return
- Unwilling to Return
- Concurrent Illness
- Lost to follow-up
- Re-operation of the affected knee joint, including revision of knee replacement components
- Incorrect implant(s)/device(s) used, device not included in protocol
- Other

Additionally, the patient may be withdrawn by the Investigator, if he/she is unable to continue participation in the study due to some condition unrelated to this study.

A Study Termination Form will be completed for all participants who withdraw from the study.

<http://ssp.intranet/sites/raqa/qms/documents/FM-CRD-029.docx>

MAKORCT-15 Final version 5.0 22 February 2018

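### Section 12.4 groups patients with undefined randomisation errors by treatment received, against the intent-to-treat label in 12.5

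*Combined protocol and SAP*

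**What the plan says.** Section 12.4 sets out the mixed model for the primary and continuous secondary efficacy variables. It then introduces a list with "The data will be summarised and comparisons presented according to", in which treatment group comes first and adverse events second. It closes with the rule "In the event of errors in randomisation, the patient will be classified according to the treatment received" and adds "All randomisation inconsistencies will be listed".

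Section 12.5 names one population: "An intent-to-treat analysis will be performed using all patients who were randomised and received a study device". It does not say that these patients are analysed in the arm assigned. No safety, as-treated or per-protocol set is defined.

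Three other sections bear on the point:

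- Section 7.0: "Any deviation from the assigned treatment will be reported as a deviation from Protocol". It gives no analysis arm for such a patient.
- Section 13.0: "No deviation from protocol may occur without Ethics Committee endorsement, unless it is required to prevent imminent harm to participants".
- Section 17.2 lists, among the reasons for not continuing in the study, "Incorrect implant(s)/device(s) used, device not included in protocol".

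**The concern.** Intent-to-treat ordinarily means that patients are analysed in the arm to which they were randomised. The only grouping rule actually written in the plan says the opposite for some patients, and which patients those are is left open. The rule could be confined to mistaken allocations, or it could be stretched to a patient who was correctly allocated but given the other implant at surgery.

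The second case matters because a change of implant may be related to prognosis. Randomisation is pre-operative (schedule in 1.0). Eligibility requires negligible lateral compartment degeneration and a functionally intact ACL (6.1). As an inference, not something the documents state, disease found at surgery to be worse than imaged would put a bicompartmental (BKR) assignment in doubt more readily than a total knee (TKR) assignment. Moving such patients to TKR leaves the BKR group without its poorer-prognosis knees, while their counterparts randomised to TKR stay where they are.

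Section 23.0 plans a formal interim analysis of functional outcomes after the 12-month visits. As worded, the scope of the rule could be settled after outcomes have been seen.

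**Working it through.** **The text.** For any patient covered by the 12.4 rule, grouping is by treatment received, which is not analysis by allocation. For a patient not covered, the label in 12.5 plausibly implies grouping as randomised, but this is not written. For a patient who departs from the assigned implant, 7.0 requires a deviation report only. Section 13.0 lets deviations occur without prior endorsement to prevent imminent harm, so they are possible.

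**The plan's own figure.** Inputs from 12.2: two-sided 0.05, difference 6.0, SD 8.0, power 80%. The plan states "For these settings a sample of 29 patients in each arm is required to achieve a power of 80" per cent. The normal approximation gives 28. The two-sample t-test gives 28.9, so 29, with power 80.1%. Then 29 × 1.2 = 34.8, so 35. The figures reproduce.

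**Bias from regrouping (illustration).** Assumptions not in the documents: no true difference; k BKR-assigned patients receive TKR and are regrouped to TKR; they and k unidentified counterparts in the TKR arm score d points below everyone else, with d = 4 to 8. With n randomised per arm, the BKR group keeps n − k patients with no deficit. The TKR group has n + k patients, of whom 2k carry the deficit. The spurious difference in favour of BKR is

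2kd / (n + k).

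Type I error comes from simulating a two-sample t-test (200,000 trials per cell, within-group SD 8).

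| n per arm | k | d = 4 | d = 8 | Type I error (d = 4, d = 8) |
|---|---|---|---|---|
| 35 | 1 | 8/36 = 0.22 | 16/36 = 0.44 | 5.10%, 5.27% |
| 35 | 3 | 24/38 = 0.63 | 48/38 = 1.26 | 5.96%, 8.69% |
| 29 | 1 | 8/30 = 0.27 | 16/30 = 0.53 | 5.06%, 5.34% |
| 29 | 3 | 24/32 = 0.75 | 48/32 = 1.50 | 6.13%, 9.29% |

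For n = 35, k = 3, d = 8, a normal approximation gives 10.09%, and holding total SD at 8 gives 8.96%. With d = 0, which represents mistakes unrelated to prognosis, bias is 0 and type I error is 4.93% to 5.04% in every cell. Grouped by allocation, simulated bias is within 0.01 of 0 and type I error is 4.1% to 5.0%.

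**Dilution from grouping by allocation.** Suppose the true difference is 6 and k of 35 BKR-assigned patients receive TKR with its full effect. The expected difference becomes 6 × (1 − k/35). The last column takes all k to be among the 29 analysed, so the effect is 6 × (1 − k/29).

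| k | Effect (of 35) | Power, 29 per arm | Power, 35 per arm | Effect and power, all k among 29 |
|---|---|---|---|---|
| 0 | 6.00 | 80.1% | 87.1% | 6.00, 80.1% |
| 1 | 5.83 | 77.8% | 85.2% | 5.79, 77.3% |
| 3 | 5.49 | 72.8% | 80.7% | 5.38, 71.1% |
| 5 | 5.14 | 67.2% | 75.5% | 4.97, 64.2% |

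**The case against.** The strongest reply is that the documents use two terms for two events. Section 12.4 speaks of errors and inconsistencies in randomisation, while 7.0 speaks of departures from the assigned treatment and sends them to deviation reporting. On that reading the rule reaches only allocation mistakes under a central system. These should be few and unrelated to prognosis, and the calculation then shows no bias. The affected patients will also be listed, so they will be visible.

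The size is assumed as well. The documents give no switch rate, no direction and no prognosis for those who switch. One switch has almost no effect. The 9% end needs three switches in the same direction, an 8-point deficit and the less natural reading, all together. The calculation uses an unadjusted t-test, whereas the planned model adjusts for baseline, so any part of the deficit carried by the baseline score would be removed.

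Much of this stands. Allocation mistakes are the natural reading, the conflict is with the usual meaning of a label rather than with an explicit as-randomised sentence, and d is best read as the deficit left after baseline adjustment. But the narrow reading is not written down. Even under it, the covered patients are taken out of their assigned arm in the efficacy comparison. A listing shows who they are but does not analyse them by allocation.

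**Conclusion.** The concern holds. The plan states a treatment-received rule in the efficacy section, without a definition and without limiting it to safety, beside a sole population labelled intent-to-treat. That part rests on the text alone.

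The consequence is conditional. It is nil if the rule touches only mistakes unrelated to prognosis, and small for a single switch. With three one-way, prognosis-related switches it is about 0.6 to 1.5 points of spurious benefit and a type I error of about 6% to 9%, under the assumed deficit of 4 to 8 points. In a trial planned on 29 evaluable patients per arm, the rule should be settled before anyone knows whether such patients exist.

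A lesser point concerns the label. The 12.5 set requires a study device to have been received, so it is a modified intent-to-treat set.

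**What to change.** 1. In 12.4 and 12.5, state that all efficacy analyses group patients by the arm assigned by the central randomisation system, whatever implant was received.
2. Remove the treatment-received rule for efficacy. Keep it for safety tables and for one labelled as-treated sensitivity analysis.
3. Define randomisation errors and separate them from departures from the assigned implant.
4. Reconcile 7.0, 12.4, 12.5 and 17.2 so that a patient given the other arm's implant stays in study follow-up and in the analysis. The 17.2 item most naturally means devices outside the protocol, and one clarifying phrase would settle it.
5. Label the 12.5 set modified intent-to-treat, and report patients randomised but not implanted by arm, with reasons.

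The cost is wording in four sections and one extra table, with no new data. Grouping by allocation gives up some power if switches occur: at 29 per arm, from 80% to about 78% with one and 73% with three. That is the price of keeping the randomised comparison.
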